3.5. CHANGES IN THE CONDUCT OF THE STUDY

The first subject was screened on 19DEC2022 under protocol Version 3.00 (dated 12OCT2022). Additional protocol versions and amendments are listed below.

Protocol version 1.00 (24-Aug-2022)

Protocol version 2.00 (22-Sep-2022); Substantial Amendment 1.00 (22-Sep-2022)

Protocol version 3.00 (12-Oct-2022); Substantial Amendment 2.00 (12-Oct-2022)

Protocol version 4.00 (28-Mar-2023); Substantial Amendment 3.00 (28-Mar-2023)

Protocol version 5.00 (06-Nov-2023); Substantial Amendment 4.00 (06-Nov-2023)

3.6. SCHEDULE OF EVENTS

Schedule of events can be found in Section 1, Table 2 of the Clinical Study Protocol (CSP). These tables are also included in APPENDIX 11 of the SAP.

3.7. CHANGES TO ANALYSIS FROM PROTOCOL

There are no changes to analysis from the protocol.

Document:	PPD		
Author:	PPD	Version Number:	1.0

Version Date: 06MAY2024

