The analysis of safety and tolerability, and functionality will be based on the safety population, which includes all subjects who receive at least one dose of study drug during the 8-week Treatment Period. The analysis of effectiveness will be based on the effectiveness population, which consists of all subjects who are enrolled, have received at least one dose of study drug, and have a Baseline and at least one post-Baseline effectiveness measurement in PANSS or CGI-S.

Percentage of subjects who discontinue for clinical reasons, ie, due to adverse event or lack of efficacy, will be summarized by presenting the number and percentage of subjects who drop out of the study for each reason. In addition, the subset of subjects who discontinue due to an AE indicative of worsening schizophrenic illness will be tabulated separately.

Percentage of subjects who discontinue for any reason (ie, “all cause discontinuation”) will be summarized by presenting the number and percentage of subjects who drop out of the study for each reason.

AEs, AEs leading to discontinuation, and serious AEs will be summarized by presenting the number and percentage of subjects with any AEs, and AEs by system organ class and preferred term. Adverse events will be further summarized by severity and by relationship to study drug. The summary of AEs will include any AE occurring on or after the first dose of study drug up to 9 days following the last dose of study drug. All AEs starting after the last dose of study drug up to 9 days following the last dose will be summarized separately.

Observed values and changes from Baseline in clinical laboratory tests (including hematology, chemistry and urinalysis), vital sign parameters (temperature, body weight, BMI, waist circumference, blood pressure [supine and standing], heart rate [supine and standing], and respiratory rate) and 12 lead ECG parameters will be summarized descriptively. The frequency of subjects with suicidal ideation and suicidal behavior based on the C-SSRS will be provided.

Measures of motor function will be assessed using the SAS, BARS, and AIMS scales. Mean changes from Baseline in these measures by scheduled visit will be presented.

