15.3.5.1. Primary and Secondary Endpoint Analysis

The primary endpoint is the percentage of subjects who discontinued for clinical reasons, such as due to AE or lack of efficacy. This percentage will be calculated by a proportion consisting of the number of subjects who experience a discontinuation event due to clinical reasons as the numerator divided by the number of subjects in the safety population as the denominator multiplied by 100 along with a corresponding 95% confidence interval (CI).

The secondary endpoint is the percentage of subjects who discontinued for any reason (ie, all cause discontinuation). The percentage will be calculated similarly as that of the primary endpoint along with a corresponding 95% CI.

The number and percentage of subjects, who discontinued early from the open-label treatment period (including both clinical reasons, ie, discontinued due to an AE (primary endpoint) and any reason for discontinuation (secondary endpoint)) will be presented.

As an exploratory analysis, the time-to-discontinuation for both clinical reason and for any reason will be summarized descriptively, (eg, n, median, 25th percentile, 75th percentile, minimum and maximum, and 95% CI on median, where possible) and presented with corresponding Kaplan-Meier plots.

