15.3.5.2. Adverse Events

Both AEs and pre-treatment events will be coded using MedDRA.

The following summaries will be provided by MedDRA SOC and PT:

- All AEs (including incidence rate and event count)
- AEs by severity (mild, moderate, severe; including incidence rate)
- AEs by relationship to study drug (related, not related; including incidence rate)

The following conventions will be followed in summarizing AEs:

- For incidence rate summaries, each subject will be counted only once within each SOC and within each PT.
- If a subject reports more than one AE within a PT and/or a SOC, the AE with the highest known severity will be used in the by severity summary. AEs with a missing severity will be assigned to the highest severity.
- For summaries by relationship to study drug, AEs will be grouped as “related” or “not related.” AEs assessed as “possible,” “probable,” or “definite,” will be grouped as “related.” AEs with a missing relationship to study drug will be regarded as related. If a subject reports more than one AE within the same SOC and PT, and any are related, the AE will be summarized as related.

Summaries of serious AEs (SAEs) and AEs leading to discontinuation will also be provided. In addition, summaries of all AEs, SAEs, and AEs leading to discontinuation by modal daily dose will be provided. The summary of AEs will include any AE occurring on or after the first dose of study drug up to 9 days following the last dose of study drug. All AEs starting after the last dose of the study drug up to 9 days following the last dose will be summarized separately. Data listings of AEs, SAEs, AEs leading to discontinuation, and deaths will be presented.

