8. OUTPUT PRESENTATIONS

[APPENDIX 1](#) shows conventions for presentation of data in outputs.

The templates provided with this SAP describe the presentations for this study and therefore the format and content of the summary tables, figures, and listings to be provided by IQVIA.

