14. STUDY MEDICATION EXPOSURE

Unless otherwise specified, the study medication exposure summary tables will include the column: SEP-363856 50 to 100 mg/day.

Exposure to study medication data will be summarized for the SAF population by the actual treatment group.

Duration of exposure (in days) will be summarized both as a continuous variable for the treatment period and categorically:

- Number and percentage of subjects with exposure $\geq 1, \geq 7, \geq 14, \geq 21, \geq 28, \geq 35, \geq 42, \geq 49$, and ≥ 56 days
- Number and percentage of subjects with exposure for 1 - 6, 7 - 13, 14 - 20, 21 - 27, 28 - 34, 35 - 41, 42 - 48, 49 - 55 and ≥ 56 days

Total person-years of exposure will be calculated for all subjects.

Mean daily dose and modal daily dose will be calculated for the treatment period and summarized.

The dose adjustment decision at each visit will be summarized in a shift table.

Lastly, the number of days that a subject received the 50 mg/day dose level, the 75 mg/day dose level and 100 mg/day dose level will be summarized for the SAF population both as a continuous variable and categorically:

- Number and percentage of subjects with exposure to a particular dose level for 1 - 6, 7 - 13, 14 - 20, 21 - 27, 28 - 34, 35 - 41, 42 - 48, 49 - 55 and ≥ 56 days

Document: PPD

Author: PPD

Version Number:

1.0

Version Date:

06MAY2024

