17.1. DISCONTINUATION DUE TO CLINICAL REASONS

Discontinuation for clinical reasons is defined as reasons due to AE or lack of efficacy. AE will follow the definition as in section [17.3](#).

The percentage of subjects who discontinued for clinical reasons will be calculated by a proportion consisting of the number of subjects who experience a discontinuation event due to clinical reasons as the numerator divided by the number of subjects in the safety population as the denominator multiplied by 100 along with a corresponding 95% confidence interval (CI).

The number and percentage of subjects, who discontinued early from the open-label treatment period (including both clinical reasons, ie, discontinued due to an AE or lack of efficacy (primary endpoint) and any reason for discontinuation (secondary endpoint)) will be presented.

The time-to-discontinuation for clinical reasons will be summarized descriptively, (eg, n, median, 25th percentile, 75th percentile, minimum and maximum, and 95% CI on median, where possible).

Time to discontinuation for clinical reasons since first dose of study medication will be plotted using Kaplan-Meier curves for the safety population by treatment group. Probability of remaining on treatment at Day 56, median time to discontinuation, and their 95% confidence intervals will be estimated using the Kaplan-Meier method for the safety population by treatment group.

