17.3.4. AEs LEADING TO DISCONTINUATION FROM STUDY

AEs leading to discontinuation from the study are those AEs with “Caused Study Discontinuation” = “Yes” on the “Adverse Events” CRF form.

AEs leading to discontinuation from the study will be summarized by SOC and PT.

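### SAP 16.7 (CGI-I) and SAP 17.8.1 (pooled C-SSRS period) are wrong as written, and SAP 3.7's declaration of no changes from the protocol is inaccurate

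*SAP*

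**What the plan says.** **CGI-I.** The protocol synopsis asks for descriptive statistics of CGI-I at each visit, Week 8 included. Protocol 15.3.6 makes change from baseline a response variable for the effectiveness scales but excepts CGI-I. SAP 16.7 opens with a description of CGI-I. Its two analysis sentences then name the CGI-S score and its change from Baseline, first by visit and then by visit within each subgroup. They match the closing sentences of SAP 16.2 (CGI-S).

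**C-SSRS.** The table in SAP 17.8.1 defines the pooled post-Baseline period as running through Visit 10, which it describes in brackets as the follow-up visit. SAP Table 1 (section 6.3), SAP 17.3, the remaining text of 17.8.1 and protocol 11.9.11 all make follow-up Visit 11. Visit 10 is Week 8, end of treatment or early termination.

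**Declared changes.** SAP 3.7 states: "There are no changes to analysis from the protocol". SAP 5.2 nevertheless defines a per-protocol population, and protocol 15.2 has only the safety and effectiveness populations. Protocol 15.3.5.2 says that "summaries of all AEs, SAEs, and AEs leading to discontinuation by modal daily dose will be provided". In the SAP text, modal dose appears only under exposure: "Mean daily dose and modal daily dose will be calculated for the treatment period and summarized". The protocol synopsis says that "the subset of subjects who discontinue due to an AE indicative of worsening schizophrenic illness will be tabulated separately". SAP 17.1 says only: "Discontinuation for clinical reasons is defined as reasons due to AE or lack of efficacy". SAP 8 adds that "The templates provided with this SAP describe the presentations for this study"; those templates are not part of the documents available here.

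**The concern.** A programmer works from the section that carries the scale's name. Following 16.7 to the letter produces the CGI-S tables a second time and no CGI-I table, although CGI-I at Week 8 is a listed endpoint.

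The C-SSRS slip sits in a safety rule. From Visit 2 onward the scale is given in its since-last-visit version, so ideation or behaviour arising after Visit 10 is recorded only at Visit 11. If the pooled period stops at Visit 10, such an event is absent from the pooled suicidality counts and from the shift in ideation score to that pooled period.

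The statement in 3.7 matters for a different reason. A reader who relies on it will not look for analyses that were added to the protocol's list, or for outputs that the SAP text leaves unstated.

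**Working it through.** No figure in the plan bears on this point. The check is a side-by-side reading, with a small count to size the C-SSRS item.

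**1. CGI-I**
- Collection (protocol Table 2): Visits 3, 4, 6, 8 and 10, that is Weeks 1, 2, 4, 6 and 8. This gives 5 post-Baseline visits and none at Screening or Baseline.
- SAP 6.2 lists the measures for which a Baseline is derived; CGI-S is there and CGI-I is not.
- SAP 16.7 with CGI-S replaced by CGI-I would request observed CGI-I and its change from Baseline. The second part has no Baseline to work from and contradicts protocol 15.3.6. The section therefore needs rewriting, not a one-letter edit.
- Elsewhere, SAP 2.2.3 keeps CGI-I as an endpoint, SAP 6.3 derives its LOCF value, and SAP 16 sets generic descriptive statistics for effectiveness outcomes.

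**2. C-SSRS pooled period**
- Scheduled post-Baseline assessments as written: V3 to V10 = 8. With follow-up included: V3 to V11 = 9.
- Subjects who roll over into SEP361-309 have no Visit 11, so nothing is lost for them. Completers who do not roll over lose 1 of 9. Early discontinuers also lose their Visit 11, and protocol 7.1 bars them from the extension.
- The number of subjects with a Visit 11 is not given. As an assumption, take the clinical discontinuation rate to lie between the mid-study 7.2% and the planning 15% (both in SAP 3.4), with 101 enrolled:
  - 0.072 × 101 = 7.27, about 7 subjects
  - 0.15 × 101 = 15.15, about 15 subjects
- These are subjects due a Visit 11 for that reason alone. They are not events. Other discontinuers and non-rollover completers add to them.
- Effect of one subject whose only event is at Visit 11: 1/101 = 0.99 percentage points, if all 101 enrolled are in the safety population.
- By-visit C-SSRS results are specified through Visit 11 and are unaffected.

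**3. SAP 3.7**
- Additions not found in the protocol's statistics section: the per-protocol population (SAP 5.2, also used in 11 and 16); PANSS response at 20%, 30% and 50% (16.1.2); PSP binary outcomes (16.5).
- Modal-dose AE summaries: the protocol names three (all AEs, SAEs, AEs leading to discontinuation). SAP 17.3 states none, and modal dose is not among its AE subgroup factors.
- Worsening-illness tabulation: promised in the protocol synopsis only. Protocol 15.3.5.1 reads "The primary endpoint is the percentage of subjects who discontinued for clinical reasons, such as due to AE or lack of efficacy" and does not repeat it. The nearest SAP outputs are 17.3.4, "AEs leading to discontinuation from the study will be summarized by SOC and PT", and the psychiatric-event listings of 17.3.12.

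**The case against.** The strongest reply is that these are drafting slips that correct themselves. The 16.7 text is plainly pasted from 16.2. The C-SSRS row names the follow-up visit in words, and the same section repeatedly identifies follow-up as Visit 11. For vital signs, AIMS and SAS, the SAP's overall post-Baseline period expressly covers follow-up, so inclusion was almost certainly intended. This is fair as to intent. It does not leave a correct rule on the page: 16.7 still lacks a usable CGI-I specification, and the C-SSRS row gives a visit number that contradicts its own label.

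On 3.7, protocol 15 leaves methodological detail to the SAP, the per-protocol population is stated openly, and the effectiveness population remains primary. That makes the additions harmless. A new analysis population is still more than detail on a method already stated, so an unqualified declaration of no changes is inaccurate.

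A reader might infer more than the documents support:
- *That CGI-I has been dropped.* It has not; the endpoint, the LOCF derivation and the generic statistics remain.
- *That the subgroup sentence in 16.7 must be wrong because SAP 7.5 names only PANSS, CGI-S and adverse events.* SAP 7.5 is not exclusive: 17.6 and 17.8.2 to 17.8.4 define further subgroup summaries, and 17.9 confirms this. Whether subgroups were meant for CGI-I is open.
- *That the modal-dose summaries were removed.* The SAP text is silent, the templates were not supplied, and 14.1 defines modal-dose categories that could serve such tables.
- *That the SAP departed from the protocol on worsening illness.* The protocol's own statistics section omits that tabulation, so the inconsistency begins inside the protocol. Discontinuation AEs by preferred term cover part of it.

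**Conclusion.** The point holds for two operative rules. SAP 16.7 does not correctly specify the CGI-I summary. SAP 17.8.1 misnumbers the follow-up visit and, if programmed by number, omits Visit 11 from the pooled suicidality counts and the pooled shift. The inaccuracy of 3.7 is secondary; it rests on the undeclared additions. The two outputs not stated in the SAP text are a gap in that text only, since either may be in the templates.

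Size: minor. The primary and secondary percentages and their confidence intervals do not depend on any of this. It would be wrong to conclude that suicidality events will be lost: that requires programming by number against the label, and at least one subject whose pooled result depends on Visit 11. The documents give no count of such subjects. The 1.0-point figure is per subject and assumes a safety population of 101.

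**What to change.** - **SAP 16.7:** specify observed CGI-I by visit, including Week 8 and the LOCF endpoint, with no change from Baseline. State whether the subgroup sentence is meant to apply to CGI-I.
- **SAP 17.8.1:** in the post-Baseline row, change Visit 10 to Visit 11 as the follow-up visit.
- **SAP 17.3 and 17.1:** state the three modal-daily-dose AE summaries and the worsening-illness tabulation, or declare their removal in 3.7. If they are already in the templates, a sentence in the SAP text saying so is enough.
- **SAP 3.7:** replace the blanket statement with a list of the additions, namely the per-protocol population, the PANSS responder analyses, the PSP binary outcomes and any others.

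The cost is SAP wording, plus at most three AE tables and one tabulation if those outputs are kept and not yet programmed. No new data collection is needed.

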4. PLANNED ANALYSES

The following analyses will be performed for this study:

- Final Analysis

4.1. DATA AND SAFETY MONITORING BOARD

There is no DSMB planned for this study.

4.2. INTERIM ANALYSIS

There is no interim analysis planned for this study.

4.3. FINAL ANALYSIS

All final, planned analyses specified in this SAP will be performed by IQVIA following Sunovion authorization of this SAP, Sunovion authorization of Analysis Populations, Database Lock

Some minor modifications may be necessary to the planned design of tables, figures, and listings to accommodate data collected during the actual study conduct.

5. ANALYSIS POPULATIONS

Agreement and authorization of subjects included/excluded from each analysis population will be conducted prior to database lock.

Enrolled subjects in 361-308 will include all subjects who signed the informed consent form (ICF) of study 361-308 and did not screen fail.

Document: PPD

Author: PPD

Version Number:

1.0

Version Date:

06MAY2024

5.1. SAFETY [SAF] POPULATION

The safety population will consist of all subjects who are enrolled and receive study medication (SEP-363856). All safety and tolerability assessments will be performed using the safety population.

5.2. PER PROTOCOL [PP] POPULATION

The per protocol (PP) population will consist of all EFF population subjects who satisfy the following conditions:

- Have 7 days or more overall exposure to study medication
- Have no important protocol deviations that can potentially impact the integrity of the effectiveness endpoint analysis

Selected effectiveness endpoints will be analyzed using the PP population. Subjects will be analyzed according to the treatment to which they receive.

5.3. EFFECTIVENESS [EFF] POPULATION

The effectiveness population will consist of all subjects who are enrolled, have received at least one dose of study medication, and have a Baseline and at least one post-Baseline effectiveness measurement in PANSS or CGI-S. Subjects will be included in the population regardless of any protocol deviation. The effectiveness population will be the primary population for the effectiveness analyses.

6. GENERAL CONSIDERATIONS

Study medication refers to SEP-363856 unless otherwise specified.

6.1. REFERENCE START DATE AND STUDY DAY

Study Day will be calculated from the reference start date and will be used to show the start/stop day of assessments and events.

Document:	PPD		
Author:	PPD	Version Number:	1.0

Version Date:

06MAY2024

Reference start date is defined as the date of the first dose of study medication (Day 1 is the Study Day of the first dose of study medication).

- If the date of assessment or event is prior to the reference start date, then:
Study Day = (date of assessment or event - reference start date).
- If the date of assessment or event is on or after the reference start date, then:
Study Day = (date of assessment or event - reference start date) + 1.

In the situation where the assessment or event date is partial or missing, Study Day and any corresponding durations will appear missing in the listings. Partial assessment or event dates will however be presented as is in the listings.

6.2. BASELINE

Unless otherwise specified, Baseline is defined as the last non-missing measurement taken prior to the first dose of study medication (including unscheduled assessments).

Whenever available, the time information should be accounted for in the derivation of Baseline values. In the case where time is not available and the date of the last non-missing measurement and the date of the first dose of study medication coincide, that measurement will be considered the Baseline.

Baseline will be derived for the following outcome measures:

- PANSS: total score, subscale scores, Marder factor scores, uncorrelated PANSS score matrix (UPSM) factor scores and total factor score, and individual item scores. For a given subject, the Baseline values for all PANSS summary and individual item scores should come from the same assessment (i.e., have the same visit number and assessment start date/time) and it should be the last assessment prior to first dose where PANSS total score is available (i.e., not set to missing). In the rare event where no PANSS total score is available before first dose due to partially completed assessments, the assessment prior to first dose with most PANSS item scores available should be taken as the Baseline assessment for all raw and derived scores as applicable.
- CGI-S score.
- BNSS: total score, subscale scores, and individual item scores. For a given subject, the Baseline values for all BNSS summary and individual item scores should come from the same assessment and it should be the last assessment prior to first dose where BNSS total score is available. In the

Document: PPD

Author: PPD

Version Number:

1.0

Version Date:

06MAY2024

rare event where no BNSS total score is available before first dose due to partially completed assessments, the assessment prior to first dose with most BNSS item scores available should be taken as the Baseline assessment for all raw and derived scores as applicable.

- SF-12 Score.
- PSP: total score, individual domain scores, and the derived binary variables. For a given subject, the Baseline values for all PSP data should come from the same assessment and it should be the last assessment prior to first dose where PSP total score is available. In the rare event where no PSP total score is available before first dose due to partially completed assessments, the assessment prior to first dose with most PSP individual domain scores available should be taken as the Baseline assessment for all raw and derived scores as applicable.
- MSQ score.
- C-SSRS: Suicidal ideation categories 1-5 (yes/no) and suicidal behavior categories 6-10 (yes/no); C-SSRS composite endpoints: any suicidal ideation (yes/no), any suicidal behavior (yes/no), any suicidality (yes/no); the suicidal ideation score (0-5). See [Section 17.8.1](#) for the definition of a C-SSRS Baseline.
- SAS: mean score and individual item scores. For a given subject, the Baseline values for all SAS summary and individual item scores should come from the same assessment and it should be the last assessment prior to first dose where SAS mean score is available. In the rare event where no SAS mean score is available before first dose due to partially completed assessments, the assessment prior to first dose with most SAS item scores available should be taken as the Baseline assessment for all raw and derived scores as applicable.
- BARS: total score and individual item scores. For a given subject, the Baseline values for all BARS summary and individual item scores should come from the same assessment and it should be the last assessment prior to first dose where BARS total score is available. In the rare event where no BARS total score is available before first dose due to partially completed assessments, the assessment prior to first dose with most BARS item scores available should be taken as the Baseline assessment for all raw and derived scores as applicable.
- AIMS: total score and individual item scores. For a given subject, the Baseline values for all AIMS summary and individual item scores should come from the same assessment and it should be the last assessment prior to first dose where AIMS total score is available. In the rare event where no AIMS total score is available before first dose due to partially completed assessments, the assessment prior to first dose with most AIMS item scores available should be taken as the Baseline assessment for all raw and derived scores as applicable.
- PSQI: global score, component scores, and individual item scores. For a given subject, the Baseline values for all PSQI summary and individual item scores should come from the same assessment and it should be the last assessment prior to first dose where PSQI global score is available.

Document: PPD

Author: PPD

Version Number:

1.0

Version Date:

06MAY2024

In the rare event where no PSQI global score is available before first dose due to partially completed assessments, the assessment prior to first dose with most PSQI item scores available should be taken as the Baseline assessment for all raw and derived scores as applicable.

- Clinical laboratory parameters (blood chemistry, hematology, urinalysis, HOMA-IR (if collected)). For a given subject, the Baseline values for the clinical laboratory parameters do not have to all come from the same assessment; the only exception is: the Baseline flag for the counts of leukocytes and its differential should be applied to records from the same assessment and it should be the last assessment prior to first dose where counts of leukocytes and its differential are reported. Baseline flag does not need to be derived for RBC morphology findings, WBC morphology findings, and urinalysis microscopic examination findings (excluding urine erythrocytes and leukocytes).
- Urine drug screening: For a given subject, the Baseline values for all urine drug screening parameters should come from the same assessment and it should be the last assessment prior to first dose where a urine drug screening test was administered.
- Vital sign parameters (supine and standing systolic blood pressure [SBP], supine and standing diastolic blood pressure [DBP], supine and standing pulse rate, respiratory rate, oral temperature), height, weight, BMI, and waist circumference. For a given subject, the Baseline values for all vital sign parameters, height, weight, BMI, and waist circumference do not have to come from the same assessment; the only exceptions are: (1) the Baseline flag for weight and BMI should be applied to records from the same assessment and it should be the last assessment prior to first dose where weight is available , (2) the Baseline flag for supine SBP and DBP, standing SBP and DBP, and the derived corresponding orthostatic endpoints (i.e., standing SBP – supine SBP; standing DBP – supine DBP) should be applied to records from the same assessment and it should be the last assessment prior to first dose where all four BP measures are available, (3) the Baseline flag for supine and standing pulse rate and the derived corresponding orthostatic endpoint (i.e., standing pulse rate – supine pulse rate) should be applied to records from the same assessment and it should be the last assessment prior to first dose where both pulse rate measures are available.
- ECG parameters: For a given subject, the Baseline values for all ECG parameters do not have to come from the same assessment. Baseline flag does not need to be derived for ECG parameters in the category of “FINDINGS”.
- Nicotine use data: Baseline of this outcome measure should be taken strictly from the assessment given at Visit 1 without regard to its temporal relationship to the first dose of study medication.
- Healthcare resource utilization data: Baseline of this outcome measure should be taken strictly from the assessment given at Visit 2 without regard to its temporal relationship to the first dose of study medication.

The Baseline flag may be derived for additional outcome measures based on the needs during analyses.

Document: PPD

Author: PPD

Version Number:

1.0

Version Date:

06MAY2024

